## BRAINII2-IMPLEMENTATION STUDY

in patients with negative biomarkers, percentage of CT requested in patients with positive biomarker, percentage of pathologic CT in patients with positive biomarker, percentage of pathologic CT in patients with negative biomarker, percentage of patients requiring admission and percentage of second ED visit after discharge.

Finally, the de-identified data from the mTBI cohort will be obtained and transferred into a web based electronic CRF(eCRF) built on RedCap to be able to be analysed. The database in RedCap will contain pseudo-anonymised clinical information about the patients with mTBI from six months prior to the implementation protocol and information from six months of the implementation protocol.

### 5.3.4. CT SCAN ANALYSIS

Brain CT scans are performed as part of the patient standard of care. CT scan findings are classified as CT negative or CT positive by local reviewers.

The criteria for CT positivity are crucial because the primary objective is related to the CT results (positive/negative). Criteria for CT-positive findings are as follows: a CT scan classified as type II or greater according to the Traumatic Coma Databank classification (range I–V), or a CT scan with the presence of the following lesions: (1) epidural haematoma, (2) subdural haematoma, (3) subarachnoid haemorrhage, (4) intraventricular haemorrhage, (5) contusion, (6) petechial haemorrhage or (7) any finding related to diffuse axonal injury and depressed skull fracture. Linear skull fractures will be recorded but not used for the definition of CT positive lesions. Subdural hypodense hygromas, calcifications, ischemia will not determine a positive qualification. Nevertheless, all findings will be recorded by. Radiologist will be trained to assess CTs regarding the following classification.

Items that WILL classify CT as positive	Items that will NOT classify CT as positive
Epidural hematoma Acute or subacute subdural hematoma  Indeterminate extra-axial hemorrhage  Subarachnoid hemorrhage Intraventricular hemorrhage Depressed cranial fracture Brain contusion (including high intensity/mixed lesions and hypodense lesions) Intraparenchymal traumatic hematoma Brain swelling Petechial hemorrhage Gliding contusions Signs of traumatic axonal injury (hyperdense lesions in brainstem or corpus callosum) Brain Swelling or oedema Compressed cisterns	Subdural hygroma Chronic subdural hematoma (no high intensity lesion inside the hematoma) All parenchymal or extraparenchymal calcifications Brain tumors Linear non-depressed fracture Cranial base fracture Pneumoencephalus  Hypodense chronic Ischemic lesions Facial fractures Scalp injury

## 6. STUDY STOPPING RULES

### 6.1. STUDY STOPPING CRITERIA FOR A PARTICIPATING SUBJECT

Participants will be excluded from the study and replaced in case of a violation of an inclusion criterion, e.g. in the mTBI group: no mild TBI, no CT scan when the patient should have received one according to the study design, no blood sampling or after 12 hours post-injury.

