1. STUDY SUMMARY

TITLE	Blood Biomarkers to improve management of mild traumatic BRAIN Injury implementation study
RUNNING TITTLE	BRAINI2 Implementation study
GENERAL OBJECTIVE	To assess the applicability and added value of a new clinical management pathway for patients with mild TBI presenting to the emergency department (ER), including the use of an in vitro diagnostic assay measuring the biomarkers GFAP and UCH-L1 in the serum, within the first 12 hours post-injury, to rule out the need for CT scan in mild TBI patients.
PRINCIPAL OBJECTIVE	
 
1) To evaluate the diagnostic performance of the VIDAS TBI (GFAP&UCH-L1) test in determining the need for CT-scan in patients with mild TBI admitted to the ER of Hospital 12 de Octubre.
 
2) To determine the safety of a management protocol including the use of the VIDAS GFAP&UCH-L1 test for patients with mTBI, in terms of complications or unforeseen neurological deterioration following the injury.
 
3) To estimate the reduction of CTs achieved using the biomarker test, by comparison with the management of TBI during the six months preceding the study (reference pathway).
 

PRINCIPAL OUTCOME	
Abnormal CT scan at admission in the ER
 
Deterioration: need for hospital admission or surgery due to TBI in the first week after TBI
 
Number of CTs prescribed in the management of mild TBI patients in the ER

PRINCIPAL OUTCOME MEASURES	
 
1) Diagnostic performance of the biomarker test
 
2) Proportion (%) of neurologic deterioration within 1 week post-TBI
 
3) Proportion (%) of CT scan prescribed in the ER over the period of the study for patients with mTBI
 

SECONDARY OBJECTIVES	
 
2.1) To determine the different times involved in the management of mild TBI patients and the effect of using the combined VIDAS test.
 
2.2) To establish differences in direct costs in the management of mild TBI in Hospital 12 de Octubre.
 
2.3.) To assess the compliance of physicians to the proposed algorithm.
 

SECONDARY OUTCOMES	
 
2.1) Time from admission to discharge. Time from admission to sample obtention. Time from venipuncture to availability of biomarker results.
 
2.2) Directs costs associated with mTBI management in the ER.
 
2.3.) Compliance with proposed algorithm.
 

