SECONDARY OUTCOME MEASURES	
 
2.1) Time differences with respect to reference group
 
2.2) Cost difference comparing before and after the implantation of the biomarker test.
 
2.3) Proportion (%) of cases in which management follow the proposed algorithm
 

METHODOLOGY	
The study will compare the different outcome measures between a historic group obtained 6 months before the initiation of the new management protocol and the group of patients admitted in the ER with a diagnosis of a mTBI after the initiation of the new bundle of care.
 
The combined GFAP&UCH-L1 test has been included in the new bundle of care of mTBI for the management in the ER of all patients with mTBI. In summary the test will be performed to all patients with mTBI admitted to the ER of Hospital 12 de Octubre and included in the new management pathway of patients with mTBI incorporated in our hospital. All patients suffering a mTBI(GCS 15-13) and admitted within 12 hours of the TBI will be included in this pathway. If the patient is included in this pathway, the prescription of cranial CT will be performed following the results of the VIDAS TBI test if the patient has had a significant TBI and a GCS of 14 or 15. Those patients with GCS of 13 or a focal neurological deficit will receive both biomarkers and CT for their management during the study period. The VIDAS TBI test interpretation as defined by the manufacturer, bioMérieux, takes into account the responses of the two biomarkers: the VIDAS TBI test is negative if the two markers GFAP and UCH-L1 are negative (below the previously defined threshold concentration for each of the biomarkers). The test is positive if at least one of the two GFAP or UCH-L1 biomarkers is positive (beyond the threshold concentration). This test is already CE marked and has already been tested on a large number of European patients and has demonstrated good safety and reliability profiles.

STUDY TYPE	Protocol evaluation Implementation Study
STUDY DESIGN	Implementation study with prospective data collection with a control reference historic group
STUDY POPULATION	Mild TBI patients with significant brain trauma admitted in the ER of Hospital 12 de Octubre

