#### 3.2. PRIMARY OBJECTIVE AND OUTCOME MEASURE

The primary objective of the study is to evaluate the performance of the two biomarkers GFAP and UCH-L1 assay to rule out the need for CT scan after mTBI.

The primary outcome will be the result of brain CT. Performance of the test will be analysed, as described in the assay instruction for use, to rule out the need for a CT scan after mTBI.

CT results will be obtained following the usual management pathway, using local radiologist report to determine the presence of pathological findings. Patients in whom no CT will be performed (i.e.: some GCS 15 without RF and GCS 14 with negative biomarkers test), will be ascribed as CT negative for the analysis if there is no deterioration or further evaluation that determines the need for a CT for other reasons.

Both GFAP and UCH-L1 biomarkers will be tested by two separate immunological assays using the usual clinical management and pathway in the management of mTBI. The positivity thresholds for each of the biomarkers and the two biomarkers' combination were validated by the company Banyan Biomarkers in an independent study, ALERT-TBI [13] and confirmed by bioMérieux using the VIDAS TBI with the same ALERT-TBI cohort and with the BRAINI study. The test will be performed if the patient is included in the new management pathway of patients with mTBI incorporated in our hospital. If the patient is included in this pathway, the prescription of cranial CT will be performed following the results of the VIDAS TBI test obtained. Patients with GCS of 13 will receive both biomarkers and CT scan for their management. Patients not following the clinical pathway (GCS<13 or non TBI patients) will be excluded from the study and managed according to routine clinical practice.

The VIDAS TBI test interpretation as defined by the manufacturer, bioMérieux, takes into account the responses of the two biomarkers: the VIDAS TBI test is negative if the two markers GFAP and UCH-L1 are negative (below the previously defined threshold concentration for each of the biomarkers). The test is positive if at least one of the two GFAP or UCH-L1 biomarkers is

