## BRAINII2-IMPLEMENTATION STUDY

positive (beyond the threshold concentration). This test has been already tested in a large number of European patients and has presented good safety and reliability profiles.

To determine the safety of the new protocol all information regarding the neurological status of the patients in relation to mTBI will be analyzed up to two weeks after the mTBI, specifically neurological deterioration, need for further observation of the patient or admission or need for treatment(medical or surgical) related to mTBI.

In order to determine the reduction of CT scans obtained with this new protocol, absolute numbers and proportions of patients finally scanned using this new protocol will be compared to the reference management of a similar number of patients during a similar historical period(i.e. data from the previous six month for patients attended for mTBI at Hospital 12 de Octubre).

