#### 3.3.2.Direct costs consumption will be obtained from each ER episode of included patients and compared to age-matched historical controls (patients managed in Hospital 12 de Octubre for mTBI in the previous six months before implementation of the new protocol).

#### 3.3.3.Assessment of the proportion of cases being managed following the proposed algorithm

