## 5.2. STUDY TIMELINE AND PLANNED MANAGEMENT ALGORITHM

All patients with TBI admitted to the ER and with a GCS between 13 and 15 will receive a blood test for biomarker determination upon admission. All patients with GCS of 13 or with a focal neurological deficit on admission will receive a CT. CTs could be performed to GCS14 and 15, independently of the result of the combined test, but the results of the test will be taken into consideration to guide for prescribing a CT. The attending physician will be responsible for the management of the patient and will have to determine the reason to prescribe CT despite normality of the biomarker test. The management algorithm that is recommended is as follows:

Risk factors (RF) include:

- Loss of consciousness.
- Posttraumatic amnesia (anterograde or retrograde).
- Advanced age (over 65)
- Antithrombotic treatment including platelet inhibitors.
- Difficulty in assessing level of consciousness: Cognitive impairment, intoxication.
- Persistent symptomatology: Repeated vomiting, persistent headache.
- High energy or High-risk mechanism: Falls over one's height, car accident, pedestrian involved in traffic accident, or accidents in which other there are other seriously injured patients.

Data will be collected directly from a specified structured form in the electronic health record of the patient. All data will be pseudonymised. Information regarding follow up will be recorded from the electronic health record regarding new contacts with the hospital or need of further assessment.

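### Section 6.1 removes patients whose due CT was not done from the whole study, so this pathway failure cannot count as non-compliance

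*Protocol*

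**What the plan says.** Section 6.1 states that participants are "excluded from the study and replaced in case of a violation of an inclusion criterion". Its examples are not having mild TBI, "no CT scan when the patient should have received one according to the study design", and having no blood sample or one drawn later than 12 hours after injury.

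The CT in question is defined elsewhere. Section 5.2 says: "All patients with GCS of 13 or with a focal neurological deficit on admission will receive a CT". The methodology part of the study summary says: "Those patients with GCS of 13 or a focal neurological deficit will receive both biomarkers and CT for their management during the study period".

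Section 3.2 has its own exclusion for departure from the pathway, but defines it by eligibility alone: "Patients not following the clinical pathway (GCS<13 or non TBI patients) will be excluded from the study".

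Three outcomes besides diagnostic performance depend on who stays in the study:

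- **Compliance**, section 3.3.3: "Assessment of the proportion of cases being managed following the proposed algorithm".
- **CT use**, section 3.2: "absolute numbers and proportions of patients finally scanned using this new protocol will be compared to the reference management", the reference being the six months before the study.
- **Safety**: the proportion of patients with neurological deterioration within one week (study summary, principal outcome measures).

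**The concern.** There are two faults. First, the label is wrong. A CT not done when due happens after entry and breaks no listed inclusion criterion. Second, the scope is too wide. Removal is from the study as a whole, yet omission of a CT that the algorithm calls for is one of the events the compliance outcome exists to count.

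The direction of bias differs by outcome:

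- **Compliance** is overstated, because the failure leaves both numerator and denominator.
- **CT proportion** in the new period can only rise when unscanned patients are deleted. The reduction against the reference period is therefore understated. The absolute number scanned does not change.
- **Deterioration** in a patient who is never scanned drops out of the safety proportion. A patient who returns and is scanned may stay in, because section 6.1 sets no time limit for the CT.

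Replacement has no function here. Section 5.1 already considers every eligible patient, over an inclusion period fixed at six months, so there is no pool of substitutes.

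**Working it through.** **Step 1: the label.** Section 6.1's examples against the eligibility lists in the study summary and section 4.1:

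| Example in 6.1 | Matching criterion |
|---|---|
| Not mild TBI | Yes (mechanism, signs or symptoms, GCS 13–15) |
| No blood sample, or later than 12 hours | Yes (sample within 12 hours) |
| Due CT not done | None |

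**Step 2: the scope.** Section 3.2 keeps some unscanned patients as CT negative, but its examples are patients for whom no CT was due. No section restricts the 6.1 exclusion to one analysis. The reference group was managed before the study, and the due CT is a rule of the study period, so no equivalent deletion is described for that group.

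**Step 3: the size.** The protocol states no figure to reproduce on this point. From section 7.1, N = 1000 tested patients. Everything else is assumed:

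- f, share with a CT due (GCS 13 or focal deficit): 3–10%
- m, share of these never scanned: 5–20%
- c, patients with another algorithm deviation: 0, 60 or 200
- p, true CT proportion: 50–90%
- deteriorations: 10 per 1000

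Patients deleted: d = N × f × m, from 1000 × 0.03 × 0.05 = 1.5 to 1000 × 0.10 × 0.20 = 20.

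*Adherence among patients with a CT due:* true value 1 − m = 95% down to 80%; reported value 100% in every case.

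*Overall compliance:* true (N − c − d)/N; reported (N − c − d)/(N − d).

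| d | c | True % | Reported % | Difference (points) |
|---|---|---|---|---|
| 1.5 | 0 | 99.85 | 100.00 | 0.15 |
| 1.5 | 60 | 93.85 | 93.99 | 0.14 |
| 1.5 | 200 | 79.85 | 79.97 | 0.12 |
| 20 | 0 | 98.00 | 100.00 | 2.00 |
| 20 | 60 | 92.00 | 93.88 | 1.88 |
| 20 | 200 | 78.00 | 79.59 | 1.59 |

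*CT proportion in the new period:* rise = p × d/(N − d).

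- d = 1.5: 0.50 × 1.5/998.5 = 0.08 points; 0.90 × 1.5/998.5 = 0.14 points.
- d = 20: 0.50 × 20/980 = 1.02 points; 0.90 × 20/980 = 1.84 points.

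*Deterioration:* true 10/1000 = 1.00%. With d = 20 and k events among the deleted patients, reported (10 − k)/980 = 1.02%, 0.92% or 0.82% for k = 0, 1 or 2.

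**Step 4: a wider trigger.** The summary and section 3.2 also say that CT prescription follows the test result, so a CT may be due for more patients. Let u be the share of all patients with a due CT omitted and v the share with another deviation. The overstatement of compliance is u(1 − u − v)/(1 − u). For u = 2% and v = 20% it is 0.02 × 0.78/0.98 = 1.6 points. For u = 10% and v = 0 it is 0.10 × 0.90/0.90 = 10 points. These rates are assumed too.

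**The case against.** The best counter-argument is about size. On the narrow reading of the trigger, the overall shifts are at most about two points, every input is assumed, and none is shown to change a conclusion. The bias in CT use works against the new pathway. Section 2.1 describes CT overuse rather than omission, and the deviation that section 5.2 anticipates, a CT despite a normal test, is untouched by section 6.1 and still counts. All of this stands, and it limits the weight of the point.

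It can also be said that omissions remain visible. The dashboard in section 5.3.3 shows the percentage of CTs requested in test-positive patients and the percentage of second emergency visits, and section 8.3 captures serious complications. But the dashboard is a monitoring tool. It is not the defined compliance outcome, and it has no indicator for GCS 13 or focal deficit. Section 8.3 does not say that excluded patients count in the deterioration proportion.

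Finally, analysis sets are usually defined in a statistical analysis plan, and none is shown. The objection here is to a rule the protocol does state: a plan that kept these patients would contradict section 6.1. The algorithm figure and the bundle of care are also not shown, so which patients the rule covers may be settled there. That is a limit on what can be read from the text, and it is why the size is given as a range.

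**Conclusion.** The point holds. The misclassification and the study-wide exclusion are plain on the text, and the direction of each bias follows without assumptions, except for deterioration, where it depends on whether events fall among the deleted patients.

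The size is unknown because the protocol gives no omission rate. On the visible trigger (GCS 13 or focal deficit) and the assumed ranges, compliance is overstated by 0.1–2.0 points overall and by 5–20 points among patients with a CT due. The CT proportion is raised by 0.1–1.8 points. Deterioration of 1.00% would be reported as 0.82–1.02%. If omissions reached 2–10% of all patients, compliance would be overstated by about 1.6–10 points.

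This should be fixed: the overall effect is probably modest, but the rule blanks out one component of a declared outcome and the correction is cheap.

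**What to change.** Reword the sentence in section 6.1:

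- Apply the missed-CT exclusion to the diagnostic-performance set only, and report how many patients it removes.
- Keep these otherwise eligible patients in the compliance, CT-use, time, cost and deterioration analyses, and count the omitted CT as non-compliance.
- Stop describing it as a violated inclusion criterion, and delete the provision for replacement.
- Identify the patients for whom a CT is due by pointing to the protocol's own algorithm, and say whether a later CT satisfies the rule.

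Eligibility, sampling, data collection and the management algorithm stay as they are. The sponsor decides whether this is a substantial change under section 10. The one drawback is that the compliance and safety figures may look slightly less favourable.

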## 7. STATISTICAL CONSIDERATIONS

### 7.1. SAMPLE SIZE

The primary endpoint of the study is to replicate the diagnostic performance of the VIDAS TBI assay to predict whether the tested patient would be positive or negative from brain injury visible on head CT scan and to determine that implementation of the VIDAS TBI, in the standard of care of patients with mTBI, is not associated with serious side effects during the six-month period of the study. We expect to test during a six-month period around 1000 patients (from the 3500 patients with suspected TBI that are admitted to our hospital yearly approximately (data from discharge diagnosis of patients with TBI related diagnostic codes)). With this sample size and with an expected prevalence of 10% of CT positivity we expect to have at least 100 patients with positive CTs. With this sample size we expect to replicate the NPV of the BRAINI study with an expected lower bound of the 2-sided 95% CI greater than or equal to 97.0%.

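### The missing-CT exclusion in section 6.1 can depend on the biomarker result; if section 3.2 decides when a CT is due, unscanned test-positives are removed, unscanned test-negatives stay, and specificity is biased upward

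*Protocol*

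**What the plan says.** Four parts of the protocol bear on a tested patient who has no CT.

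- **Section 6.1** excludes and replaces participants who violate an inclusion criterion. One of its examples is "no CT scan when the patient should have received one according to the study design". The inclusion criteria in sections 1 and 4.1 cover mechanism, signs, symptoms, GCS and blood sampling within 12 hours. None requires a CT.
- **Section 3.2**, on prescribing: for patients in the pathway, "the prescription of cranial CT will be performed following the results of the VIDAS TBI test obtained".
- **Section 3.2**, on scoring: patients without a CT count as CT negative unless they deteriorate or later need one. A bracket introduced by 'i.e.' names them as "some GCS 15 without RF and GCS 14 with negative biomarkers test".
- **Section 5.2**: everyone with GCS 13 to 15 is tested, and CT is stated outright for GCS 13 or a focal deficit. For GCS 14 and 15, "the results of the test will be taken into consideration to guide for prescribing a CT", and the attending physician decides.

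Diagnostic performance of the test is the first principal outcome measure in section 1. The only numerical target, in section 7.1, concerns the NPV.

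**The concern.** Whether a CT was due is the condition for exclusion under section 6.1, and the text answers that question in two ways for GCS 14 and 15. Under section 3.2 a positive result leads to a CT, so a test-positive patient without one was due a scan and is removed. Under section 5.2 the result only guides the physician, so it is arguable that no CT was strictly due and the patient stays.

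Under the first reading, staying in the analysis depends on the index test. An unscanned test-negative patient is kept and scored as a true negative; an unscanned test-positive patient is deleted. Most of those deleted would be expected to be false positives, because section 7.1 expects only 10% CT positivity. Deleting them shrinks the denominator of specificity and leaves its numerator intact. Two analysts following the same text could therefore report different specificities from the same records.

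**Working it through.** **Inputs from the protocol (section 7.1).** "We expect to test during a six-month period around 1000 patients" and "with an expected prevalence of 10% of CT positivity we expect to have at least 100 patients with positive CTs". CT-positive = 1000 × 0.10 = 100, which reproduces the protocol's figure. CT-negative = 1000 − 100 = 900.

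**Assumptions, because the protocol gives no value.** True specificity is 30%, 40% or 50%. The share u of false positives left unscanned is 5% to 30%. All test-negatives are retained.

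**Formula.** Kept: specificity = TN / 900. Removed: specificity = TN / [TN + FP × (1 − u)].

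At 40%, TN = 360 and FP = 540:

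- u = 5%: 27 removed, 360 / 873 = 41.2%
- u = 10%: 54 removed, 360 / 846 = 42.6%
- u = 20%: 108 removed, 360 / 792 = 45.5%
- u = 30%: 162 removed, 360 / 738 = 48.8%

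Reported specificity across the assumed range:

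| True specificity | TN | FP | u = 5% | u = 10% | u = 20% | u = 30% |
|---|---|---|---|---|---|---|
| 30% | 270 | 630 | 31.1% | 32.3% | 34.9% | 38.0% |
| 40% | 360 | 540 | 41.2% | 42.6% | 45.5% | 48.8% |
| 50% | 450 | 450 | 51.3% | 52.6% | 55.6% | 58.8% |

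The rise is 1.1 to 1.3 points at u = 5%, 2.3 to 2.6 at 10%, 4.9 to 5.6 at 20% and 8.0 to 8.8 at 30%. For scale, the half-width of a 95% interval for 40% of 900 is 1.96 × √(0.4 × 0.6 / 900) = 3.2 points.

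**Other measures.** Take specificity 40%, an assumed sensitivity of 95% (TP = 95, FN = 5) and u = 10%.

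- *NPV* = 360 / (360 + 5) = 98.6% either way, because it uses test-negatives only.
- *PPV* with nobody removed = 95 / 635 = 15.0%. If scans are missed regardless of lesion status and those patients are removed, 85.5 / (85.5 + 486) = 15.0%, unchanged. If only false positives are removed, 95 / (95 + 486) = 16.4%.
- *Sensitivity*, if 10% of true positives are also unscanned and removed: 85.5 / (85.5 + 5) = 94.5%. From 99% it would fall to 89.1 / (89.1 + 1) = 98.9%.

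**What keeping these patients can do.** Suppose 10% of all test-positives are unscanned, all are kept, and none of their lesions shows itself in follow-up. The 9.5 unscanned true positives are then scored as false positives. Specificity = 360 / (900 + 9.5) = 39.6%, PPV = 85.5 / 635 = 13.5% and sensitivity = 94.5%. Keeping them therefore has its own smaller error in specificity, and an error in PPV.

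**The case against.** The strongest reply is that sections 3.2 and 6.1 may not overlap. A reader might infer that 3.2 scores, and 6.1 removes, the same unscanned test-positive patient. The text does not establish this. The bracket in section 3.2 opens with 'i.e.', and for GCS 14 it names test-negatives only. The overlap is confined to test-positive GCS 15 patients without risk factors, and only if the words on a negative test attach to GCS 14 alone. If they attach to both groups, there is no direct contradiction. But section 6.1 is then the only rule that could reach unscanned test-positives, so the dependence on the test result remains.

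Other stronger readings also fail:

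- *That false positives disappear.* Only unscanned ones could be removed; scanned false positives stay.
- *That PPV is necessarily inflated.* It is unchanged if missed scans are unrelated to lesions.
- *That the study expects unscanned test-positives.* Section 5.3.3 lists "percentage of CT requested in patients with positive biomarker" as an indicator. Measuring a proportion does not show that it is expected to fall below 100%.
- *That the sample-size target is at risk.* Section 7.1 aims at an NPV with an "expected lower bound of the 2-sided 95% CI greater than or equal to 97.0"%. Removing test-positives does not touch it.

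Two further replies carry weight. The algorithm figure is not visible in the copy reviewed and Appendix 1 is a separate file, so either may define when a CT is due. That could settle which reading applies, but sections 3.2 and 5.2 would still differ. If the algorithm makes a CT due after a positive result, section 6.1 selects on that result. Second, follow-up by record review may miss lesions in test-positives, so keeping them is not free of bias.

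**Conclusion.** The concern holds in limited form. Section 6.1 makes a post-enrolment event, which no inclusion criterion mentions, a ground for exclusion. If section 3.2 determines when a CT is due at GCS 14 and 15, that exclusion depends on the index test and specificity is biased upward. The size is about 1 point if 5% of false positives are unscanned and removed, 2 to 3 points at 10%, and about 5 to 6 points at 20%. These figures rest on 900 CT-negative patients from section 7.1, an assumed specificity of 30% to 50%, and an unscanned share that the protocol does not give. If nearly every test-positive patient is scanned, the effect is negligible. Sensitivity may fall slightly. The issue affects a principal outcome measure, though not its rule-out target, and should be corrected.

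**What to change.** 1. In section 6.1, remove the missing-CT ground as a reason for leaving the diagnostic-performance set. Keep every validly tested patient whatever the result.
2. In section 3.2, assign the status of every unscanned patient by the follow-up rule already there, and state explicitly that it covers both test results.
3. Report the number unscanned by test result.
4. Show specificity, sensitivity and PPV with unscanned test-positives included and excluded. State that follow-up may miss lesions in this group, so neither version is free of error.
5. Reconcile sections 3.2, 5.2 and 6.1 on when a CT is due at GCS 14 and 15. That clinical decision belongs to the authors.

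The cost is wording in these sections and one sensitivity analysis on data already being collected. Reported specificity may be slightly lower.
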